1. INTRODUCTION

This statistical analysis plan describes the plan for presenting the data for final analysis for Protocol ALXN1820-SCD-201. Due to the early termination of the study, data will only be listed.

Safety, pharmacokinetic (PK), pharmacodynamic (PD), immunogenicity, biomarker, demographics and baseline characteristics, medical history, prior and concomitant medications and efficacy data are included. Standard data presentation instructions and listing specifications are contained in the Data Presentation Plan in a separate document.

Changes to the protocol-planned analyses are described in Section 4.5.

Due to the early termination of the study, Cohort 3 will not be initiated, the planned interim analysis will not be conducted, and the output of all participants will be listed without inclusion of tables and figures.

1.1. Objectives, Endpoints, and Estimands

The objectives and endpoints of ALXN 1820-SCD-201 are summarized in [Table 1](#)

Table 1: Objectives and Endpoints

Objectives	Endpoints
Primary	
To assess the safety and tolerability of ALXN1820 SC in participants with SCD	Safety assessed by incidence of TEAEs and SAEs, physical examination, vital sign measurements, clinical laboratory, and electrocardiogram results through Day 211 (Cohorts 1 and 2)
Secondary	
To assess the multiple-dose PK of ALXN1820 SC	Serum ALXN1820 multiple-dose PK profiles through Day 211 (Cohorts 1 and 2)
To assess the PD effects of ALXN1820 SC	Change in serum concentrations of total and free properdin over time through Day 211 (Cohorts 1 and 2) Change in CAP activity using the Wieslab AP assay through Day 211 (Cohorts 1 and 2)
To assess the effect of ALXN1820 on complement biomarkers	Change from Baseline in complement biomarkers through Week 12 (Cohorts 1 and 2)
To assess the effect of ALXN1820 on hemolysis biomarkers	Change from Baseline in hemoglobin levels at Week 12 (Cohorts 1 and 2) Change from Baseline in hemolysis markers (e.g., lactate dehydrogenase, reticulocytes, and bilirubin and hemopexin) at Week 12 (Cohorts 1 and 2)
To assess the immunogenicity of ALXN1820 SC	Incidence of ADAs to ALXN1820 through Day 211 (Cohorts 1 and 2)
Exploratory	
To explore the effect of ALXN1820 on VOC markers	Change from Baseline in VOC-related biomarkers through Week 12 (Cohorts 1 and 2)

Table 1: Objectives and Endpoints

Objectives	Endpoints
To explore the clinical efficacy of ALXN1820 SC in SCD	VOC events (rate of VOC, time to first VOC) through Week 12 (Cohorts 1 and 2)

Abbreviations: ADA = antidrug antibody; AP = alternative pathway; CAP = complement alternative pathway; PD = pharmacodynamic; PK = pharmacokinetic(s); SAE = serious adverse event; SC = subcutaneous; SCD = sickle cell disease; TEAE = treatment-emergent adverse event; VOC = vaso-occlusive crisis.
 Note: Estimand is not applicable.

1.2. Study Design

This is a Phase 2a study, with up to 3 multiple-dose cohorts of open-label ALXN1820 subcutaneous (SC) in adult participants with sickle cell disease (SCD; HbSS and HbSβ⁰-thalassemia).

The study is planned to be conducted in up to 30 adults participants with SCD enrolled in up to 3 open-label cohorts (Cohorts 1, 2, and 3 [optional]) to receive multiple SC doses of open-label ALXN1820. At the time of the early termination of the study, 2 participants are enrolled in the study. ALXN1820 is administered as described in [Table 2](#).

Table 2: ALXN1820-SCD-201 Dosing Cohorts

Cohort	N	Study Intervention	Route of Administration	Planned Dose	Number of Doses/Dose Interval
1	Up to 12 Maximum of 6 on a stable dose of hydroxyurea	ALXN1820	SC	300 mg	QW × 13
2	Up to 12 Maximum of 6 on a stable dose of hydroxyurea	ALXN1820	SC	600 mg	Q4W × 4

Abbreviations: N = number of participants; QW = once weekly; Q4W = once every 4 weeks; SC = subcutaneous; SCD = sickle cell disease

The dose and dosing intervals for Cohorts 1 and 2 were determined using cumulative safety data, an interim PK/PD analysis from participants enrolled in Study ALXN1820-HV-101, and data from the 6-month Good Laboratory Practice toxicology study in monkeys.

Cohorts 1 and 2 run in parallel, and participants are randomized 1:1 to either of the cohorts upon determining eligibility. Each cohort is to be stratified to ensure participants with SCD who are treated with a stable dose of hydroxyurea and participants with SCD who are not currently treated with hydroxyurea are included. The Treatment Period is 12 weeks for Cohorts 1 and 2.

For participants who were previously treated with hydroxyurea but are not currently on hydroxyurea, treatment is to be stopped at least 30 days prior to providing informed consent.

This study uses an independent Data Monitoring Committee to monitor safety and to perform the planned interim analyses of the study. At Alexion's discretion and after consultation with the Data Monitoring Committee, additional participants with SCD may be enrolled as replacement participants if a participant discontinues during the Dosing Period for reasons other than drug-related adverse events (AEs).

2. STATISTICAL HYPOTHESES

Not applicable.

3. ANALYSIS SETS

Due to the early termination of the study, no analysis set will be defined except Enrolled Set, which includes all participants who signed the informed consent form, excluding screen failures. All the listing outputs will be based on the Enrolled Set.

4. STATISTICAL ANALYSES

4.1. General Considerations

All analyses will be performed using Statistical Analysis Software[®] (SAS[®]) Version 9.4 or higher (SAS Institute Inc., Cary, NC, USA) or other validated statistical software.

Baseline is defined as the last nonmissing observation before the first dose of the study intervention.

Treatment Period is 12 weeks for Cohorts 1 and 2. Follow-up Period is 18 weeks after the last dose or may be longer if CAP activity is below the normal range or 80% of the baseline value, as defined in the protocol.

Study and participant characteristics (e.g., disposition, demographics and baseline characteristics, medical history, and protocol deviations) are described in Section 6.2.

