Cohort 1 and Cohort 2 will run in parallel, and patients will be randomized 1:1 to either of the cohorts on determination of eligibility. The decision to initiate Optional Cohort 3 will be made at Alexion's discretion and will be based on analysis of PK/PD and safety after at least 8 patients from Cohorts 1 and 2 (4 from each cohort) have enrolled. Furthermore, enrollment of Optional Cohort 3 will start after Cohorts 1 and 2 are fully enrolled. Each cohort will be stratified to ensure patients with SCD who are treated with a stable dose of hydroxyurea and patients with SCD who are not currently treated with hydroxyurea are included. The Treatment Period will be 12 weeks for Cohorts 1 and 2, and 6 weeks for Cohort 3. For patients who were previously treated with hydroxyurea but are not currently on hydroxyurea, treatment must have been stopped at least 30 days prior to providing informed consent.

At Alexion's discretion, and after consultation with the Data Monitoring Committee (DMC), additional participants with SCD may be enrolled as replacement participants if a participant discontinues during the Dosing Period for reasons other than drug-related adverse events (AEs).

Disclosure Statement This is an open-label, parallel group intervention study with up to 3 treatment arms.

Number of Participants:

Up to 30 adult patients with SCD (HbSS and HbSβ⁰-thalassemia) will be enrolled in up to 3 cohorts and will receive multiple open-label SC doses of ALXN1820. The cohorts will enroll both patients with SCD who are being treated with a stable dose of hydroxyurea and patients with SCD who are not currently treated with hydroxyurea. For patients who were previously treated with but are not currently on hydroxyurea, treatment must have been stopped at least 30 days prior to providing informed consent.

Intervention Groups and Duration:

The planned study duration is approximately 38 weeks for Cohorts 1 and 2: up to 56 days (8 weeks) for Screening, 84 days (12 weeks) for the Treatment Period, and 126 days (18 weeks) for the Follow-up Period. Patients will attend outpatient visits during the Treatment and Follow-

up Period with the option to stay at the inpatient facility. The end of study (EOS) for each individual patient is anticipated to be Day 211 (210 days) or the timepoint at which complement activity has returned to a normal range or 80% of baseline if later than Day 211.

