- ^l Injection site reaction evaluation will be conducted on dosing days and if a reaction occurs, the evaluation will continue until the reaction is fully resolved.
- ^m Blood samples for biomarkers will be collected 2 times prior to receiving the first dose (collect once during Screening and then again at Day 1 pre-dose, the 2 collections should be at least 2 weeks apart). Collection of blood (for serum, citrated and K2-EDTA, or P100 plasma) and urine.
- ⁿ In case of any suspected case of hypersensitivity or anaphylaxis additional samples for the assessment of ADA may be collected at or near the time of the event.
- ^o If a VOC occurs, samples will be collected as per unscheduled visit.
- ^p The patient will record symptoms of VOC in a paper diary throughout the study. The Investigator or qualified designee will review the patient diary at every visit.
- ^q The Investigator or qualified designee will meet with the participant at each visit to ensure they carry the clinical study participant safety card at all times and to review the potential meningococcal infection risks of ALXN1820, and to address any safety concerns of the participant.
- ^r Collection of adverse events and serious adverse events will begin after ICF signing.
- Abbreviations: ADA = antidrug antibody; BMI = body mass index; CAP = complement alternative pathway; ECG = electrocardiogram; HiB = *Haemophilus influenzae* type B; HIV = human immunodeficiency virus; ICF = informed consent form; IEC = Independent Ethics Committee; K2-EDTA = dipotassium ethylenediaminetetraacetic acid; MCV4 = tetravalent meningococcal conjugate vaccine; NA = not applicable; PD = pharmacodynamic(s); PK = pharmacokinetic(s); QW = once weekly; VOC = vaso-occlusive crisis.

Table 4: Schedule of Activities – Screening Through Day 85 (Cohort 2) – Q4W Dosing

Study Day	Screening Day –56 to Day –1	Day 1	Day 15	Day 29	Day 43	Day 57	Day 71	Day 85
Window (Day)	NA	NA	± 3	± 3	± 3	± 3	± 3	± 3
Informed consent ^a	X							
Eligibility criteria ^b	X	X						
Randomization ^c		X						
Confirmation of or administration of meningococcal vaccination ^d	X							
Confirmation of or administration of HiB and S pneumoniae vaccination	X							
Medical history and demographics	X							
Physical examination	X	X						
Abbreviated physical examination				X		X		X
Height, weight, and BMI ^e	X	X		X		X		X
Hematology ^f	X	X		X		X		X
Clinical chemistry ^f	X	X		X		X		X
Coagulation ^f	X	X		X		X		X
Hepatitis B and C screen	X							

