Hospitalization for elective treatment of a pre-existing condition that did not worsen from baseline is not considered an AE.

3. Schedule of Activities: Tables 3, 4, and 7 footnotes:

- Blood samples for biomarkers will be collected two times prior to receiving the first dose (collect once during Screening and then again on Day 1 pre-dose, the 2

collections ~~should~~ **must** be at least ~~2~~ **1** weeks apart). Collection of blood (for serum, citrated and K2-EDTA, or P100 plasma) and urine.

4. Schedule of Activities: Tables 3, 4, and 7 footnotes:

° Randomization will occur following confirmation of all eligibility requirements.

Randomization can be performed up to 1 business day prior to Day 1 dosing.

5. 8.2.2. Vital Signs

Vital sign measurements will be taken after the participant has been resting in the supine or semi-recumbent position **or preferred position per site standard practice** for at least 5 minutes and will include temperature (tympanic or oral), respiratory rate, ~~supine~~ blood pressure, and pulse. Ideally, the same arm for each participant should be used for BP and pulse measurements. Orthostatic (standing) blood pressure will only be measured at Screening.

6. Schedule of Activities: All Tables footnotes

- At Screening, supine and standing (orthostatic) blood pressures will be performed. **At all other visits blood pressure can be performed supine or preferred position per site standard practice.**

7. Schedule of Activities: All Tables footnotes

- If a VOC occurs, samples will be collected as per unscheduled visit, **when feasible.**

Please file this letter and any IRB/EC correspondence with all copies of the protocol in the Investigator Site File and in all pertinent repositories in which the protocol is maintained.

If there are any questions concerning these changes, please contact us. These changes will also be captured in any future protocol amendment.

[REDACTED]
[REDACTED], Clinical Development Sciences
Alexion Pharmaceuticals
Phone: [REDACTED]
Email: [REDACTED]

Cc: eTMF

[REDACTED], Clinical Project Lead

Alexion Pharmaceuticals, Inc.

14 July 2023

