4.3.2. Analysis of SCD Biomarkers

Absolute value, change from Baseline, and percent change from Baseline in biomarkers, including Ba, C3a, C4a, C5a, sC5B9, LDH, bilirubin (total, direct and indirect), reticulocytes (absolute and percent), haptoglobin and hemopexin will be listed over time for each participant.

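### Should biomarker baseline be the mean of the Screening and Day 1 draws instead of the last pre-dose value?

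*SAP*

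**What the plan says.** Protocol section 1.3, footnote m to Table 3 (repeated under Tables 4 and 7), states: "Blood samples for biomarkers will be collected 2 times prior to receiving the first dose". One draw is at Screening and one is pre-dose on Day 1, and "the 2 collections should be at least 2 weeks apart". Administrative Change Letter #2, item 3, keeps both draws, halves the minimum gap to one week and makes it mandatory. The upper limit on the gap comes from the Synopsis, which allows "up to 56 days (8 weeks) for Screening".

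SAP section 4.1 sets a single rule: "Baseline is defined as the last nonmissing observation before the first dose of the study intervention". Only immunogenicity has its own definition (section 4.3.3), and that is also a last-value rule. SAP section 4.3.2 plans to list, over time for each participant, "Absolute value, change from Baseline, and percent change from Baseline in biomarkers, including Ba, C3a, C4a, C5a, sC5B9, LDH, bilirubin" and further hemolysis markers. Section 4.4 does the same for hemopexin and nitric oxide. Neither section makes an exception for the second pre-dose draw, and section 4.5 does not mention it.

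SAP sections 1, 1.2 and 4.5 say that two participants were enrolled when the study was terminated, that data will only be listed, and that descriptive statistics have been dropped.

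**The concern.** In Table 3 the PK, PD and ADA samples begin on Day 1, while the dedicated biomarker row also has a Screening draw with a required separation. No complement or VOC marker is an eligibility criterion, so that draw is not a screening test. The natural inference is that two draws were meant to characterise the pre-treatment level. A last-value baseline then appears to discard half of that information.

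There is no untreated arm, so each participant's pre-dose level is the only comparator. Noise in a single Day 1 value passes into every listed change for that person, and in a percent change it enters both numerator and denominator. Participants may have had 1 to 10 VOCs in the past year and a recent one is not excluded, so one draw could be atypical. With independent errors, the loss would equal the information from a third more participants in a full cohort (1/0.75 = 1.33, or 12 participants doing the work of 16). The samples are already scheduled, so the remedy looks free.

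**Working it through.** **The plan's own figure.** Protocol section 9.2 and SAP section 5 state 88% power for a 1 g/dL hemoglobin change, SD 1 g/dL, n = 12, two-sided 0.05. A one-sample t-test with 11 degrees of freedom and noncentrality √12 × 1/1 = 3.46 gives 88.3%, so the figure reproduces. It concerns hemoglobin, not the biomarkers, and serves below only as a scale.

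**Best case: independent errors.** Let s² be the within-person variance at each visit.

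- Last value: Var(change) = s²(1 + 1) = 2s².
- Mean of two: Var(change) = s²(1 + 1/2) = 1.5s².
- Variance ratio 0.75; SD ratio √0.75 = 0.866, a 13.4% reduction.

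Applied to the hemoglobin calculation for scale only, power would move from 88.3% to 90.2%, 92.0%, 93.7% or 95.3% if 25%, 50%, 75% or 100% of the variance of change were independent visit-to-visit noise.

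**Serially correlated errors.** The two draws are 1 to 8 weeks apart, so independence cannot be taken for granted. Assume equal variances and a weekly first-order autoregressive correlation ρ, with the draws g weeks apart and the post-dose visit t weeks after Day 1. In units of s²:

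- Last value: 2 − 2ρ^t.
- Mean of two: 1 + (1 + ρ^g)/2 − ρ^t − ρ^(t+g).
- Difference (last minus mean): (1 − ρ^g)(1/2 − ρ^t).

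Averaging therefore helps only when ρ^t < 1/2. At Week 12 this means ρ below 0.5^(1/12) = 0.944; at Week 2 it means ρ below √0.5 = 0.707.

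SD of change, mean of two divided by last value:

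| Weekly ρ | Week 12, gap 1 wk | Week 12, gap 8 wk | Week 2, gap 1 wk | Week 2, gap 8 wk |
|---|---|---|---|---|
| 0 | 0.866 | 0.866 | 0.866 | 0.866 |
| 0.5 | 0.935 | 0.867 | 0.957 | 0.913 |
| 0.7 | 0.962 | 0.876 | 0.999 | 0.995 |
| 0.9 | 0.992 | 0.956 | 1.040 | 1.210 |
| 0.95 | 1.001 | 1.007 | 1.050 | 1.302 |

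One cell in full, ρ = 0.9, g = 1, t = 2: last value 2 − 2(0.81) = 0.380; mean of two 1 + 0.95 − 0.81 − 0.729 = 0.411; SD ratio √(0.411/0.380) = 1.04.

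The documents give no within-person SD or correlation for any marker, so the row of the table that applies is unknown.

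**What reaches the output.** With two participants, no means, no intervals and no tests, the effect on any planned estimate is nil. Only individual listed changes would differ. SAP section 4.3.2 lists absolute values over time and does not exclude Screening, so both pre-dose values can appear beside the changes. If Day 1 is missing, the Screening value becomes the baseline.

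**The case for a change.** The strongest case for changing the rule is that the protocol paid for a second draw, section 9.4 promised that the SAP would deal with unused data, and the SAP already averages triplicate ECGs before computing change. At Week 12, the timepoint of the hemolysis endpoints, averaging helps or is close to neutral for weekly correlations up to 0.95. One sentence would do it.

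Part of this stands: the SAP could have said how it treats the Screening draw, and does not. The rest is weaker.

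- No document states the purpose of the two draws or calls for a mean, so the SAP contradicts nothing.
- Triplicate ECGs are same-day readings at one time point, and averaging them removes recording noise. Screening and Day 1 may be eight weeks apart, and a mean then mixes an older state with the current one.
- The complement endpoint runs through Week 12 with samples from Day 15, so the early visits where averaging can do harm are included.
- LDH, bilirubin, reticulocytes, haptoglobin and hemopexin belong to the hematology and chemistry panels (Protocol section 10.2, Table 13), whose rows carry no two-draw gap rule. SAP section 4.2.2 also lists their changes from baseline as safety data. A separate mean baseline in section 4.3.2 would give the same result two baselines and two changes.
- Abnormal Screening laboratory values may be repeated at the investigator's discretion (Protocol section 5.4), so a mean of all pre-dose values could include selectively repeated ones.
- This SAP was written after termination of an open-label study, so a new baseline rule would be open to the charge of being post hoc.

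**Conclusion.** No change follows. The observation is accurate: with a Day 1 value present, the Screening biomarker value enters no change or percent change. The loss is at most 13.4% of the SD of change, under independent and equally variable errors around a stable level. Under the assumed autoregressive correlation the benefit falls to nothing and turns into a penalty, 4% to 21% at Week 2 with a weekly correlation of 0.9 and a gap of one to eight weeks. Last value versus mean is a fair trade-off between closeness to dosing and averaging of noise, and the plan chose a clear, reproducible rule that is the same for efficacy and safety listings. With two participants and listings only, no conclusion depends on it. An analyst who lists every pre-dose value, as section 4.3.2 permits, lets the reader compare the two draws directly. In a full cohort with estimated mean changes, the choice would deserve an explicit argument.

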4.2. Primary Endpoints Analysis

The primary endpoint for the study is safety, which will be assessed by the following parameters:

- AEs
- Clinical laboratory assessments
- Vital signs
- Physical examination
- Electrocardiogram (ECG) parameters, including heart rate (HR), PR, RR, QRS, and QT intervals and corrected QT interval by Fridericia's formula (QTcF)

4.2.1. Analysis of AEs

All the AEs will be listed for each participant.

The adverse event will be presented using primary Medical Dictionary for Regulatory Activities (MedDRA) System Organ Classes (SOCs) and Preferred Terms (PTs) according to the version of the MedDRA coding in effect dictionary at the time of database lock. The SOCs will be presented in alphabetical order, and the PTs will be presented in descending order of frequency overall within each SOC.

Treatment-emergent adverse events (TEAEs) (refer to Section 6.1 for the definition of TEAE) will be indicated. The following information of AEs will also be listed:

- Relationship as assessed by the investigator
- Severity by severity grades according to the National Cancer Institute (NCI) Common Terminology Criteria for Adverse Events (CTCAE, v5.0) (Grade 1, Grade 2, Grade 3, Grade 4, Grade 5)
- Seriousness criteria
- VOC exacerbated
- Leading to discontinuation from study intervention

- Leading to study withdrawal
- Leading to death
- Injection site reaction (ISR) according to the Investigator.

Clinically significant ISR will be reported as AE and will be indicated on the AE listing.

4.2.2. Analysis of Laboratory Assessments

Laboratory results based on standardized units will be used.

Absolute values and changes from Baseline in clinical chemistry, hematology, coagulation, and urinalysis will be listed at each visit.

Clinical chemistry, hematology, coagulation, and urinalysis values will be graded according to NCI CTCAE, v5.0, where applicable, and will be listed.

4.2.3. Analysis of Vital Signs

Vital sign measurements include body weight, systolic blood pressure (SBP), diastolic blood pressure (DBP), HR, temperature and respiratory rate (RR). Actual values and change from Baseline in vital sign measurements will be listed at each visit for each participant.

Abnormal vital signs will be listed for each participant, criteria for abnormal vital signs are defined as follows:

- Body weight $\geq 7\%$ decrease from Baseline; Body weight $\geq 7\%$ increase from Baseline
- SBP < 90 mmHg; SBP > 140 mmHg; SBP > 160 mmHg
- DBP < 50 mmHg; DBP > 90 mmHg; DBP > 100 mmHg
- HR < 60 beats per minute; HR > 100 beats per minute
- Temperature < 36 degrees Celsius; temperature > 38 degrees Celsius
- RR < 12 breaths per minute; RR > 20 breaths per minute

4.2.4. Analysis of Physical Examination

All physical examination data will be provided in data listings. Abnormal physical examination finding during the study will be listed.

4.2.5. Analysis of ECG Results

The ECG parameters include HR, PR, RR, QRS, and QT intervals and QTcF. The mean of the triplicate ECG readings at the timepoints collected will be calculated. Absolute value and change from Baseline values will be listed at each visit for each participant. Change from Baseline values will be based on the calculated mean at each timepoint.

Outlier ECG results will be listed for each reading per visit, criteria for outlier ECG results are defined as follows:

- QT interval and QTcF > 450 msec

- QT interval and QTcF > 480 msec
- QT interval and QTcF > 500 msec
- QT interval and QTcF increases from Baseline > 30 msec
- QT interval and QTcF increases from Baseline > 60 msec

All ECG individual measurements as well as the calculated mean of triplicate ECG readings, will be provided in data listings.

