Review patient diary ^p	X	X	X	X	X	X	X	X	X	X	X	X	X	X
Review safety card ^q	X	X	X	X	X	X	X	X	X	X	X	X	X	X
Concomitant medications	←Monitor continuously (after ICF is signed)→													
Adverse events ^r	←Monitor continuously (after ICF is signed)→													

^a Signed and dated IEC-approved informed consent must be obtained before any study-specific screening procedures are performed.

^b Eligibility will be assessed at Screening and Day 1.

^c Randomization will occur following confirmation of all eligibility requirements.

Table 3: Schedule of Activities – Screening Through Day 85 (Cohort 1) – QW Dosing

- ^d To reduce the risk of meningococcal infection (*Neisseria meningitidis*), all patients will be vaccinated with MCV4 and serogroup B meningococcal vaccinations at least 14 days before dosing, if not already vaccinated within 3 years before the first dose (or per national/local guidelines). Participants who initiate study intervention treatment less than 14 days after receiving a meningococcal vaccine must receive treatment with appropriate prophylactic antibiotics until at least 2 weeks after vaccination. Every effort should be made to start the meningococcal vaccination series at least 14 days prior to randomization.
- ^e Height and BMI only at Screening.
- ^f Non-fasting blood samples will be obtained.
- ^g Serum pregnancy test is required for all female participants of childbearing potential (ie, have achieved menarche) to confirm that a female participant is not pregnant prior to first dosing. A urine pregnancy test can be performed if the Screening visit is within 3 weeks of Day 1 visit. A urine (or serum if required by local site policy) pregnancy test is to be performed at all other required timepoints.
- ^h At Screening, supine and standing (orthostatic) blood pressures will be performed.
- ⁱ Predose triplicate 12-lead ECGs will be performed on Day 1 only and will be performed 3 times at approximately 2, 1, and 0.5 hours before the start of dosing (If this schedule is not feasible, ECGs performed with at least 20 min apart is acceptable). If the scheduled dosing is delayed, predose ECGs performed within 4 hours of dosing do not need to be repeated. Postdose ECGs will be performed within 30 min before PK/PD sample collection.
- ^j PK and PD samples are collected at pre-dose and between 2 and 4 hours post dose.
- ^k PD samples will be collected to assess serum total and free properdin and CAP activity.

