8.2.3. Electrocardiograms

Triplicate 12-lead ECGs will be recorded at the time points described in the SoA (Section 1.3) to obtain heart rate, PR, QRS, and QT intervals. 12-lead ECG recordings will be made after the participants have been resting in a supine position for at least 10 minutes.

At each time point at which triplicate ECGs are required, 3 individual ECG tracings should be obtained as closely as possible in succession but no more than 2 minutes apart.

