9.4.3.1. ECG Analysis

Cardiac assessments will be performed in the Safety Population.

The ECG parameters will be measured at the specified time points, including heart rate, PR, RR, QRS, QT, and QTcF intervals. The average of the triplicate ECG readings at the time points collected will be calculated, and changes from pretreatment baseline values will be assessed by each cohort and treatment arm.

An outlier analysis will be performed that will summarize the absolute count, frequency and percentage of participants who meet any of the following outlier criteria at each visit by cohort and treatment arm:

- QT, QTcF interval > 450 msec
- QT, QTcF interval > 480 msec
- QT, QTcF interval > 500 msec
- QT, QTcF interval increases from baseline > 30 msec

- QT, QTcF interval increases from baseline > 60 msec

Analysis of drug-related QT/QTc interval changes relative to plasma PK concentrations may be conducted on all dose regimens. The principles of this analysis follow the statistical methods described by Garnett et al. (Garnett, 2018).

Detailed analysis will be specified in the SAP or a separate ECG analysis plan.

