4.5. Changes to Protocol-Planned Analyses

Due to the early termination of the study and limited enrolled participants, data will only be listed. Applicable changes from Protocol Amendment 1.0 are as follows:

- The interim analyses have been removed

- The Cohort 3 will not be initiated and have been removed
- Analysis sets have been removed except for Enrolled Set, all analyses will be based on the Enrolled Set
- Analyses of PK parameters have been removed
- Summary descriptive statistics will not be provided
- Outlier analyses of ECG have been removed
- Inflammatory biomarkers and cell adhesion biomarkers have been removed from the analysis of VOC-related biomarkers
- Visit windows have been removed

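### Does listing QT/QTcF outliers by single tracing, while change from baseline uses the triplicate mean, spoil the ECG safety output?

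*SAP*

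**What the plan says.** SAP Section 4.2.5 has the mean of the triplicate readings calculated, and specifies: "Change from Baseline values will be based on the calculated mean at each timepoint". It then says "Outlier ECG results will be listed for each reading per visit" and gives five criteria. Three are absolute, starting with "QT interval and QTcF > 450 msec" and rising to 480 and 500 msec. Two are increases, "QT interval and QTcF increases from Baseline > 30 msec" and the same above 60 msec. The section ends by placing all individual measurements and the triplicate means in data listings.

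SAP Section 4.5, the list of departures from the protocol, contains the bullet "Outlier analyses of ECG have been removed". The analysis it refers to is in Protocol Section 9.4.3.1. There, "The average of the triplicate ECG readings at the time points collected will be calculated", change from baseline is assessed, and an outlier analysis reports the number and percentage of participants meeting each criterion at each visit.

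SAP Section 4.1 takes baseline as the last nonmissing value before first dose, with no separate ECG rule. Protocol Section 8.2.3 says that at each triplicate time point "3 individual ECG tracings should be obtained as closely as possible in succession but no more than 2 minutes apart". Footnote i to Tables 3, 4 and 7 of the Schedule of Activities has pre-dose triplicate ECGs done three times on Day 1, at about 2, 1 and 0.5 hours before dosing, and allows a fallback: "ECGs performed with at least 20 min apart is acceptable".

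SAP Sections 1 and 1.2 record early termination with 2 participants enrolled, and output limited to listings.

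**The concern.** ECG results are one of the five components of the primary safety endpoint in SAP Section 4.2. Triplicates are recorded to average out tracing-to-tracing noise. Flagging on single tracings appears to give that up: one noisy tracing in three can mark a timepoint whose mean is unremarkable.

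The two increase criteria raise a further question. The SAP defines change from baseline only for the mean, so it does not say how a single tracing would be compared with baseline, and two programmers could build different listings.

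Section 4.5 then appears to remove the very output that Section 4.2.5 specifies. Because it has a separate bullet dropping summary statistics, the ECG bullet could be read as removing the outlier listing as well.

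Finally, the pre-dose ECGs might be three triplicate sets or three single tracings. On the second reading, the last-observation rule would set one baseline tracing against post-dose means. With only two participants, each shown line by line, a stray flag would be conspicuous.

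**Working it through.** **Direction.** A mean of three readings cannot exceed a threshold unless at least one reading does. Flagging by tracing therefore catches every timepoint that flagging by mean would catch, and usually more. Nothing is missed, and the only cost is extra flags.

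**Number of opportunities.** Tables 3, 4 and 6 of the protocol schedule post-baseline ECGs on Days 15, 29, 57, 85, 99, 155 and 211, which is 7 days. Two participants give 2 × 7 = 14 timepoints and 14 × 3 = 42 tracings at most, leaving aside any Day 1 post-dose or unscheduled ECG.

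**Extra flags for an increase above 30 msec, no drug effect.** The documents give no QTcF variability, so the SDs are assumptions: 6 to 10 msec between timepoints (B) and 5 to 8 msec between replicates (R). Baseline is the mean of the last pre-dose set. On the mean, SD of change = √[2(B² + R²/3)]. At B = 8, R = 6 this is √[2(64 + 12)] = 12.3 msec, and P(change > 30) = 1 − Φ(30/12.3) ≈ 0.75%, which matches the simulation. The any-of-three rates come from simulation.

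| B, R (msec) | Mean > 30 | Any of 3 readings > 30 | Difference | × 14 timepoints |
|---|---|---|---|---|
| 6, 5 | 0.07% | 0.42% | 0.35% | 0.05 |
| 8, 6 | 0.76% | 2.45% | 1.69% | 0.24 |
| 10, 8 | 2.72% | 7.40% | 4.68% | 0.66 |

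The ratio is about 2.7 to 6, but it is a ratio of small numbers: less than one extra flag in the whole study.

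**Absolute thresholds.** Here the per-reading wording plainly applies, and the result depends on how near the participant's true level is to the limit. With replicate SD 10 msec and no other variation, P(any reading > 450) against P(mean > 450) is 6.7% against 0.03% at a true level of 430 msec, and 40.4% against 4.2% at 440 msec. The second case means about 14 × (0.404 − 0.042) = 5.1 extra flagged timepoints if both participants sat at 440 msec throughout. In that case the listed means would show a stable value near 440.

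**Section 4.5 against Section 4.2.5.** Section 4.5 opens by saying that data will only be listed, and its bullets are changes from the protocol. The protocol's outlier analysis was a table of counts and percentages. Dropping that table and keeping a listing satisfies both sections. The PK bullet works the same way: parameter analyses are removed, while Section 4.3.1 still lists concentrations.

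**Baseline.** Footnote i and Protocol Section 8.2.3 fit together if each of the three pre-dose times carries a triplicate set. The 2-minute limit then applies within a set and the 20-minute gap between sets. Under the SAP, baseline is the last set, averaged like any other timepoint. Averaging all three sets at B = 8, R = 6 would lower the SD of change from 12.3 to √[76 + 76/3] = 10.1 msec, about 18%, only if sets taken within two hours vary as independently as visits weeks apart. If the between-timepoint part is day-to-day variation shared by the three sets, the SD is √[76 + 64 + 36/9] = 12.0 msec, a gain of about 3%.

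**The case for a change.** The strongest case for acting is that the text is unclear in a component of the primary endpoint and would take only a few sentences to repair. Three parts of it stand. The unit for the increase criteria is not stated outright. The Section 4.5 bullet is poorly worded beside a listing that remains. The SAP gives immunogenicity its own baseline rule but gives ECG none. Per-tracing flags could also be numerous for a participant close to 450 msec, and at a true increase of 20 msec with replicate SD 10 the rates for an increase above 30 msec are 42.8% by any reading and 11.1% by mean.

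The claim that the output is contradictory and over-flags does not stand. The sentence basing change on the mean comes immediately before the outlier sentence, so a programmer has a ready reading: means for the increase criteria, readings for the absolute ones. Over-flagging presupposes that the mean is the correct unit, yet Protocol Section 9.4.3.1 ties averaging to change from baseline and does not name the unit for outliers. In a safety listing, screening each tracing is a legitimate preference for sensitivity. No rate, participant count or test is built on the flags, and the means are listed for comparison.

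**Conclusion.** No change to the plan follows. What remains is a clerical slip in one bullet, and a gap over the unit and baseline that analysts can fill sensibly from the surrounding text. The choice of reading or mean trades sensitivity against noise. For increases above 30 msec with no drug effect, the cost is about 0.05 to 0.66 extra flags over 14 scheduled timepoints. Around absolute thresholds it may be several, but only for a participant whose QTcF is already close to the limit.

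These sizes rest on assumed SDs, normal errors and full attendance by both participants. The conclusion rests on firmer ground: two participants, listings only, no inference on safety, and every tracing shown with its triplicate mean. It would be different if the study had continued to tables of outlier counts by cohort, where the unit of flagging would alter reported percentages.
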